	10.1. CONSORT diagrams	
	10.2. Covariate balance figures	
	, , , ,	4-

2. Abstract

This trial emulation study aims to emulate the FLAURA trial (NCT02296125) using real-world specialty oncology electronic health records data and to investigate the concordance between the trial's original and the emulated treatment effect estimate on overall survival (OS). FLAURA was a Phase III, double-blind, randomised study assessing the efficacy and safety of AZD9291 (= osimertinib, 80 mg orally, once daily) versus a standard of care (SoC) Epidermal Growth Factor Receptor (EGFR) Tyrosine Kinase Inhibitor (TKI) (either gefitinib [250 mg orally, once daily] or erlotinib [150 mg orally, once daily]) in patients with locally advanced or metastatic EGFR sensitizing mutation (EGFRm+) Non-small Cell Lung Cancer (NSCLC) who are treatment-naïve and eligible for first-line treatment with an EGFR-TKI.

3. Amendments and updates

Version date	Version number	Section of protocol	Amendment or update	Reason
July 22, 2024	V1.0	NA	Initial version	NA
September 26, 2024	V1.1	Context and rationale for data sources, Context and rationale for covariates, Data analysis, Context and rationale for analysis plan	 Added more details to covariate encoding Specified that EDB1 will be used for primary analysis Provided reasons for excluding EDB2 and EDB4 from primary analysis Added sensitivity analyses 	
October 7, 2024	V1.2	Context and rationale for analysis plan	Added a complete case sensitivity analysis	
November 17, 2024	V1.3	Various	Incorporated FDA team feedback	

4. Rationale and background

Randomized controlled trials (RCTs) are generally regarded as the gold-standard of evidence for establishing efficacy of medical products. However, real-world data (RWD) are increasingly used to complement evidence from RCTs. Yet, to have confidence in the accuracy of non-interventional studies medical products and their outcomes in oncology, investigators need to know what questions can be validly answered, with which non-interventional study designs, and which analysis methods

are appropriate, given the data that is available. Building on a process from the RCT DUPLICATE initiative¹⁻⁴ **Emulation of Comparative Oncology trials with Real-world Evidence** (**ENCORE**) is the trial emulation discussed in this protocol is part of the expansion project specific to oncology and aims to emulate 12 randomized oncology RCTs using multiple EHR data sources.

The purpose of this protocol is to describe the emulation of the **FLAURA trial**.^{5,6} FLAURA was a Phase III, double-blind, randomised study assessing the efficacy and safety of AZD9291 (= osimertinib, 80 mg orally, once daily) versus a standard of care (SoC) Epidermal Growth Factor Receptor (EGFR) Tyrosine Kinase Inhibitor (TKI) (either gefitinib [250 mg orally, once daily] or erlotinib [150 mg orally, once daily]) in patients with locally advanced or metastatic EGFR sensitizing mutation (EGFRm+) Non-small Cell Lung Cancer (NSCLC) who are treatment-naïve and eligible for first-line treatment with an EGFR-TKI.

The primary trial estimate targeted for emulation is a hazard ratio (HR) for death (overall survival) of 0.80 (95% CI 0.64 to 1.00) with a median overall survival time of 38.6 months (95% CI 34.5 to 41.8) in the osimertinib group and 31.8 months (95% CI, 26.6 to 36.0) in the comparator group. Market availability of osimertinib began April 18, 2018 based on the progression-free survival (PFS) endpoint.

The PFS endpoint was published in the NEJM on November 18, 2017 (PMID 29151359).5

The OS endpoint was published in the NEJM on November 21, 2019 (PMID 31751012).6

5. Research question and objectives

The primary and secondary research question is summarized in Table 1.

A. Primary research question and objective

Table 1. Primary and secondary research questions and objective.

Objective:	To compare the overall survival [OS] in patients who initiated osimertinib versus patients who initiated erlotinib or gefitinib.			
Hypothesis:	Initiation of osimertinib improves overall survival time as compared to initiation of erlotinib or gefitinib			
Population (mention key inclusion-exclusion criteria):	 Age at least 18 years Locally advanced or metastatic Non-small Cell Lung Cancer (NSCLC) patients who receive treatment without curative intent The line of therapy for patients in EDB1 and EDB2 is implicitly advanced/metastatic because the line of therapy classification starts after their advanced/metastatic diagnosis in the respective database In EDB4, patients must explicitly have any evidence of a metastasis prior initiating Osimertinib, gefitinib or erlotinib. 			

	Adenocarcinoma histology		
	EGFR sensitizing mutation (any EGFRm+)		
	Treatment-naïve and eligible for first-line (1L) treatment with an EGFR-targeted tyrosine kinase inhibitor (TKI)		
	• ECOG 0 or 1		
Exposure:	Initiation of osimertinib		
Comparator:	Initiation of erlotinib or gefitinib		
Outcome:	Time to all-cause mortality (OS)		
Time (when follow up begins and ends):	From the day of treatment initiation until death or last observed clinical activity/last sign of the patient being alive or data cut-off, whichever occurred earlier		
Setting:	1L EGFRm+ metastatic NSCLC		
Main measure of effect:	Primary: Hazard ratio (95% CI) for overall survival		
	Secondary: median overall survival time (difference) in % (95% CI)		

The emulation of the main protocol elements of the FLAURA is illustrated side by side in **Table 2**.

Table 2. Trial emulation table summarizing the main protocol elements of the FLAURA trial and the planned emulation.

Protocol component	FLAURA RCT	Emulation	
Eligibility criteria	 - Age at least 18 years at time of randomization - Adenocarcinoma of the lung - Locally advanced or metastatic NSCLC, not amenable to curative surgery or radiotherapy - Tumour harbours one of the 2 common EGFR mutations known to be associated with EGFR-TKI sensitivity (Ex19del, L858R), either alone or in combination with other EGFR mutations - Patients must be treatment-naïve for locally advanced or metastatic NSCLC and eligible to receive first-line treatment with gefitinib or erlotinib 	there needs to be evidence of metastatic disease at time of treatment initiati (EDB4) - Evidence of any EGFR mutation in the 180 days before/on treatment initiati - Treatment needs to be first-line for advanced (EDB1) or metastatic (EDB2) disease or patients with prior exposure to any potential antineoplastic treatment	
Treatment	 World Health Organization Performance Status of 0 to 1 No prior treatment with any systemic anti-cancer therapy for locally advanced/metastatic NSCLC No prior treatment with an EGFR-TKI. osimertinib versus SoC EGFR-TKI (erlotinib or gefitinib) 	osimertinib versus SoC EGFR-TKI (erlotinib or gefitinib)	
strategies Assignment procedures	Random assignment to receive either osimertinib or SoC EGFR-TKI (gefitinib or erlotinib) in a 1:1 ratio	1:1 matching of patients based on their propensity to initiate osimertinib as opposed to SoC EGFR-TKI	
Follow-up period	Time from randomization until death from any cause or censoring of patients who did not die on the basis of the last recorded date that the patient was known to be alive	Time from treatment initiation until death from any cause or censoring of patients who did not die on the basis of the last recorded date that the patient was known to be alive	
Outcome	Overall survival	Overall survival	
Causal contrast	Intent-to-treat effect	Counterfactual comparison of initiation of osimertinib as opposed to SoC EGFR-TKI	

6. Research methods

6.1. Data sources

6.1.1. Context and rationale for data sources

The overall ENCORE project uses data from a total four different oncology-specific electronic health records (EHR)-derived data sources: ConcertAl, COTA, Flatiron Health, McKesson/Ontada. For ENCORE, not all databases are available for each cancer indication and the names of the databases will henceforth be blinded and referred to as ENCORE DataBase (EDB) 1, 2, 3 and 4 (the numbering does not coincide with the above order of mention of the databases).

For this trial emulation, NSCLC-specific data are available for EDB1, EDB2 and EDB4.. The fitness-for-purpose of the data for the given trial emulation were assessed and considered for the final selection of the databases.

Reason for selection: All considered databases draw from a comprehensive national sample of patients with cancer in the US with detailed EHR-derived information on the information necessary to study medication effectiveness in oncology.

Strengths of data source(s): Size and detailed clinical information on oncology-specific variables and outcomes (validated composite all-cause mortality sourced from different data sources^{7,8}).

Limitations of data source(s): General limitations across all data sources include missing data, potential lack of data continuity, heterogeneous data provenance, quality/heterogeneous ascertainment of mortality endpoint data and the variability in how line of treatment is captured and curated (a more comprehensive discussion of the data sources and approaches is provided in section 7. After a comprehensive assessment of all data sources regarding their fitness for the purpose of emulating the FLAURA trial, EDB2 and EDB4 were found insufficient to be included in the main analysis for the following reasons.

- Rationale for excluding of EDB2 from primary analysis: After applying all I/E criteria, EDB2 results in a cohort with the very small sample size even before matching (Figure 7). Compared to EDB1 and EDB4, there is also an absence of important prognostic covariates which may lead to biased effect estimates due to unmeasured confounding. In addition, EDB2 did not show sufficient balance in measured covariates (Figure 10).
- Rationale for excluding of EDB4 from primary analysis: As shown in Table 3, the patient identification period in EDB4 starts on 10/01/2018 which is after the official approval of osimertinib for 1L metastatic EGFRm+ NSCLC. This means there are limited "control" patients captured in EDB4 from the pre-osimertinib era (see Figure 15). Given the documented clinical benefit and the corresponding rapid uptake of osimertinib after April 2018, it could be assumed that patients who initiated the "old" standard-of-care after April 2018 did so for specific reasons. This means these patients may be likely to be significantly different in their baseline characteristics and prognosis for reasons that may not be measurable.

For these reasons, only EDB1 will be used for the main analysis. However, EDB2 and EDB4 will be considered as part of a sensitivity analysis in which all databases are individually analyzed and treatment effect estimates are pooled using a meta-analytic fixed effects model (see sensitivity analysis #11 in Table 9).

Data source provenance/curation: In brief, all databases provide EHR-derived oncology-specific patient-level information which are either derived directly (e.g., through structured data fields and dropdown menu selections) from EHR and/or undergo semi-automated abstraction processes from unstructured reports. The detailed data provenance, abstraction processes and implemented business rules to curate and prioritize certain variables may vary by database and can be found in legacy publications by the data partners.

Table 3. Metadata about data sources and software.

ie 5. Metadata about data soui	EDB1	EDB2	EDB4
Data Source(s):	EHR-derived	EHR-derived	EHR-derived
Study Period:	Patient identification period: 01/01/2011-04/30/2024 with follow-up information through data cut-off date on 04/30/2024	Follow-up information through 02/24/2023 (there is no specific time period restrictions for patient eligibility)	Patient identification period: 10/01/2018-09/30/2023 with follow-up information through data cut-off date on 09/30/2023.
Eligible Cohort Entry Period:	Anytime at start of study drug initiation	Anytime at start of study drug initiation	Anytime at start of study drug initiation
Data Version (or date of last update):	Delivery: Jul 11, 2024	Delivery: Sep 8, 2023 Updated (LoT addition): Mar 11, 2024	Delivery: Oct 24, 2023 Updated (demographics): Feb 29, 2024
Data sampling/extraction criteria:	Patients are sampled if they have a confirmed diagnosis of advanced NSCLC via abstraction on or after 1 Jan 2011, and at least 2 EHR visits on or after 1 Jan 2011. Both ICD-9 (162.x) and ICD-10 (C34x or C39.9) codes are used for the initial selection, and advanced diagnosis are then confirmed via abstraction (since ICD codes do not specify advanced diseases).	Patients are sampled if they were diagnosed with NSCLC and do not meet any of the following exclusion criteria: patient is <18 years of age at the time of diagnosis, does not have the malignancy of interest, is not evaluated at the accessible provider site for the malignancy of interest, has concurrent primary malignancies, has no date of diagnosis in EHR, patient chart has no clinician note available in the EHR, is diagnosed with a malignancy after the diagnosis of the malignancy of interest prior to evaluation for the malignancy of interest at the accessible provider site, is only seen once at the provider site for the malignancy of interest, is initially misdiagnosed and treated for another malignancy, but was later confirmed to have the malignancy of interest, is on therapy, active surveillance, or observation for a malignancy diagnosed prior to the diagnosis of the malignancy of interest at the time of diagnosis of the malignancy of interest, is metastatic (includes leukemias and multiple myeloma) for a malignancy diagnosed prior to the malignancy of interest, with the	NSCLC Patients with an office visit in the reporting period will be included in the report with full patient history. Patients are sampled if they were diagnosed with NSCLC and with a documented visit date, within the defined reporting period, to one of the network facilities and were at least 20 years of age at the time of first diagnosis. Patients who were on a clinical trial at any point in their treatment history are excluded.

		presence of low grade (inclusive of grades 1 and 2) neuroendocrine histology	
Type(s) of data:	EHR-derived	EHR-derived	EHR-derived
Data linkage ¹ :	Mortality/date of death is a composite endpoint of structured and unstructured data from the EHR, obituary data, and the social security death index	Mortality/date of death is a composite endpoint of structured and unstructured data from EHRs and commercially available obituary data including the Social Security Administration death master file	Mortality/date of death is a composite endpoint of structured EHR data and linked commercial data from clearinghouse providers hosted by Datavant.
Conversion to CDM ² :	No	No	No
Software for data management:	R 4.3.2	R 4.3.2	R 4.3.2

¹ Mortality/date of death is a composite endpoint that is often derived from various linked sources including social security death index/ Social Security Administration death master file, obituary data and EHR records

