6.6.2. Context and rationale for study inclusion criteria

Study inclusion criteria were defined to emulate all key inclusion criteria for the trial that were deemed both clinically relevant and measurable in EHR data. See Excel appendix table 1 (Table1_I_E) for a one-by-one evaluation. A summary of the operational definitions of the inclusion criteria that were applied for each database can be found in the Excel appendix table 2. A flowchart of the study cohort assembly is provided in Appendix 3.

In the RCT, 95% of patients were metastatic at date of randomization while only the remaining 5% were locally advanced, not amenable to curative surgery or radiotherapy. Since locally advanced line settings are readily curated in EDB1 only, we will restrict the analysis in EDB2 and EDB4 to only patients with any evidence of metastases prior to or on index date (more details see below in 6.4.4).

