6.6.5. Context and rationale for outcome(s) of interest

The primary outcome for the database study was defined to emulate the primary outcome for the trial, time from index to death due to any reason (overall survival). Operational definitions:

- EDB1: Time in {days, months and years} from index date to death due to any reason. The date of death is de-identified to month-level granularity or (rarely) to year-level granularity and the date of death is therefore imputed to the 15th of a month or mid-year/July 2 of the year of death, respectively. In If there is no indication that a patient died during the study period, the patient is censored. The censoring date is defined as the last visit or treatment encounter or data cut-off date, whichever occurred earlier. The overall survival endpoint is operationalized using a parameterized R function edb1_get_os() and more details can be found in the attached pdf documentation.
- EDB2: Time in {days, months and years} from index date to death due to any reason. If there is no indication that a patient died during the study period, the patient is censored. The censoring date is defined as the last observed activity date or data cut-off date, whichever occurred earlier. Activity dates are defined as documented in Table 4. Dates used to derive time to all-cause mortality may have some associated imprecision such that the date of death is either known completely, the year and month is known or only the year is known. The overall survival endpoint is operationalized using a parameterized R function edb2_get_os() and more details can be found in the attached pdf documentation.

Table 4. Relevant clinical activities considered to derive last activity date for censoring.

Table / clinical activity considered	Dates considered
Adverse events	Event date
Therapy (cellular, systemic, radiation, surgery)	Start and end dates or declined intervention date, surgery date, assessed resection dates
Palliative care referral	Referral date
Visits	Contact/visit date
Vitals	Assessed date
Labs	Lab date
Biomarkers	Specimen collection date
Patient observation period	Start and end dates
Demographics	Date of most recent contact with provider, date patient was diagnosed with a second primary malignancy
Performance assessments	Documented date, reported date

[figure not shown]
Secondary diagnoses	Diagnosis date
Progression, histology, lymphovascular invasion, metastatic sites, pancoast tumor, perineural invasion	Assessed date

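### Does the EDB1 primary analysis need a sensitivity analysis that removes patients who started erlotinib or gefitinib after April 2018?

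*Protocol*

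**What the plan says.** Section 6.1.1 gives the reason for leaving EDB4 out of the primary analysis. Its identification period begins on 1 October 2018, after first-line approval, so there are few control "patients captured in EDB4 from the pre-osimertinib era". The section adds that anyone who still began erlotinib or gefitinib after April 2018 may have done so for particular reasons, and that "these patients may be likely to be significantly different in their baseline characteristics and prognosis for reasons that may not be measurable".

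EDB1 alone is used for the primary analysis. Table 3 gives its "Patient identification period: 01/01/2011-04/30/2024" and, for cohort entry in all three databases, "Anytime at start of study drug initiation".

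Three rows of Table 9 bear on calendar time or choice of database:

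- #9 drops osimertinib starters before 18 April 2018.
- #10 restricts entry to 2015 to 2022.
- #11 brings in EDB2 and EDB4. Section 6.1.1 describes it as an analysis in which "all databases are individually analyzed and treatment effect estimates are pooled using a meta-analytic fixed effects model".

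The rationale of #10 reports an abrupt fall in use of the older drugs after approval and almost no overlap of the arms across 2018. Section 7 goes further and treats calendar year as a perfect predictor of treatment.

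**The concern.** The protocol names a group of controls whose prognosis may differ in ways matching cannot repair, and uses that to set one database aside. The database it keeps admits the same kind of patient for six years after approval. Row #9 applies a cut at the approval date to the osimertinib arm only, with no counterpart for the controls.

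The study judges agreement with the trial's hazard ratio of 0.80. If late starters had an unusual prognosis and were numerous, they could move the EDB1 estimate, and no planned analysis inside EDB1 would show it. Row #11 helps only indirectly, because EDB4 differs from EDB1 in other ways:

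- Population: "we will restrict the analysis in EDB2 and EDB4 to only patients with any evidence of metastases prior to or on index date".
- Sampling in EDB4: "Patients who were on a clinical trial at any point in their treatment history are excluded".
- Censoring: in EDB1, "The censoring date is defined as the last visit or treatment encounter or data cut-off date, whichever occurred earlier" (section 6.6.5), whereas EDB4 uses the last recorded vital signs or data cut-off.

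**Working it through.** **Is the reasoning inconsistent?** The objection to EDB4 concerns the make-up of its control arm. Nearly all EDB4 identification falls after approval, so late starters would dominate that arm. EDB1 identification starts on 1 January 2011, more than seven years before approval. The protocol does not say that a minority of late starters spoils a control arm, and its wording about them is tentative. Choosing EDB1 follows from the argument.

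**How large could the group be?** The count would be in Figure 13, which is not available here, so the share is an assumption. Months are days/30.44:

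- 1 Jan 2011 to 18 Apr 2018: 87.5
- 18 Apr 2018 to 30 Apr 2024: 72.4
- Under #10, 1 Jan 2015 to 18 Apr 2018: 39.5 (45% of 87.5)
- Under #10, 18 Apr 2018 to 31 Dec 2022: 56.4 (78% of 72.4)

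Assume a constant control start rate in each era, the later being r times the earlier. Share before matching = r × post / (pre + r × post). For r = 0.05 this is 3.62/91.1 = 4.0%.

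| r | Primary | Under #10 |
|---|---|---|
| 0.02 | 1.6% | 2.8% |
| 0.05 | 4.0% | 6.7% |
| 0.10 | 7.6% | 12.5% |
| 0.20 | 14.2% | 22.2% |

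The abrupt fall and near-absence of overlap favour the upper rows.

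**What precision does the primary analysis have?** Section 10.3 states 80% power at a hazard ratio of 0.8 and two-sided alpha 0.05, without an event count in the readable text. Schoenfeld's formula with 1:1 allocation gives 4 × (1.960 + 0.842)² / (ln 0.8)² = 630.5 events, so the stated power corresponds to about 631. The standard error of the log hazard ratio is √(4/630.5) = 0.080.

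**How far could late starters move the estimate?** The documents give no hazard for this group, so multipliers of 0.8, 1.5 and 2.0 relative to other controls are illustrations. The model uses exponential survival, a control median of 31.8 months (section 4), true hazard ratio 0.80, uniform entry within each era and administrative censoring only. Expected event fractions by 30 April 2024 are 0.908 for early controls, 0.497 for late controls and 0.432 for osimertinib. A simulation with 800,000 patients per arm gave the change in log hazard ratio on removing late starters. The estimate with them included is 0.80 × exp(−change).

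| Share | Change (0.8, 1.5, 2.0) | Estimated hazard ratio |
|---|---|---|
| 1.6% | −0.002, 0.005, 0.008 | 0.802, 0.796, 0.794 |
| 4.0% | −0.006, 0.012, 0.021 | 0.805, 0.790, 0.783 |
| 7.6% | −0.012, 0.023, 0.040 | 0.810, 0.782, 0.769 |
| 14.2% | −0.023, 0.044, 0.075 | 0.819, 0.766, 0.742 |

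A cruder approximation, 0.80 / k^share with multiplier k, ignores the late starters' shorter follow-up and gives larger shifts: at 5% and k = 2, 0.80/2^0.05 = 0.773.

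**Could the extra analysis detect such a shift?** Suppose each late control is removed with one osimertinib patient. With share s, the fraction of events lost is s(0.497 + 0.432) / [(1 − s) × 0.908 + s × 0.497 + 0.432]. At s = 0.04 this is 2.8%, leaving 613 events. The standard error of the change is √(4/remaining − 4/630.5).

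| Share | Events left | Power | SE of change | Change / SE |
|---|---|---|---|---|
| 4.0% | 613 | 79% | 0.0135 | 0.4, 0.9, 1.6 |
| 7.6% | 596 | 78% | 0.019 | 0.6, 1.2, 2.1 |
| 14.2% | 566 | 76% | 0.027 | 0.9, 1.6, 2.8 |

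Seven of these nine shifts are below two standard errors. The standard error is also too small: section 6.7.1 matches without replacement within a caliper of 1% of the propensity score standard deviation, separately in each imputed dataset, so removing some controls can re-pair others and add noise.

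**The case for a change.** The strongest argument for acting is that the protocol raised this selection itself, says it may be unmeasurable, and then offers no look at it inside the primary database. That is factually correct. Row #9 leaves late controls untouched. Row #10 drops those starting in 2023 and 2024 but also removes everyone from 2011 to 2014, so under the constant-rate assumption their share rises. Row #11 supplies a separate EDB4 estimate, where the group is concentrated, but mixes in the database differences. A date filter and a re-match would cost little, and perfect prediction by calendar year cannot be literal, since #9 exists because a few patients received osimertinib early.

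What stands is that such an analysis could be added. It does not follow that its absence is an error. The filter would remove nearly all concurrent controls, so the comparison would lean almost entirely on the section 7 assumption that calendar time affects survival only through treatment, which the protocol admits cannot be tested. A changed hazard ratio could then reflect selection of late starters or calendar time, with no means of separating them. A cut at the approval date would also discard controls who started days later, for whom special reasons need not apply.

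**Conclusion.** The concern does not hold. EDB4 is set aside because it lacks controls from before osimertinib, and EDB1 supplies them, so the protocol does not contradict itself. Carried out as written, the EDB1 analysis is not undermined by a small minority of late starters. At the shares the text favours (about 4% or less), the shift in the hazard ratio is under 0.02 in the simulation. The cruder formula gives up to about 0.03 at 5%. The largest change in log hazard ratio at 4%, 0.021, is about a quarter of the primary analysis's standard error of 0.080.

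This rests on assumed start rates and hazard multipliers, on roughly 631 events inferred from the stated power, and on the protocol's description of a sharp fall in use of the older drugs. Late starts clustered soon after approval would have longer follow-up and somewhat more weight than modelled. A share near 14% with a doubled hazard would matter more (0.74 against 0.80), but nothing in the readable text suggests a group that large. What remains is a preference for a thirteenth sensitivity analysis with its own interpretive problem.

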6.6. Setting

6.6.1. Context and rationale for definition of time 0 (and other primary time anchors) for entry to the study population

Time 0 in this database study is defined as the date a patient initiated osimertinib (exposure) or erlotinib or gefitinib (comparator) as part of their 1L systemic antineoplastic treatment for advanced or metastatic NSCLC. This aims to emulate the date of randomization and cohort entry in the RCT (the time from randomization to first dose is not reported in the clinicaltrials.gov study report or the trial articles).

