• EDB4: For the EDB4 database, the following logic is applied (see Figure 2). First, patients are identified who have ever initiated any of osimertinib, erlotinib or gefinitib. If patients initiated more than one of these three regimens simultaneously, these patients are not considered and will be excluded. To guarantee that the osimertinib, erlotinib or gefinitib are initiated in a 1L metastatic setting, patients are only considered if there is any evidence of a metastatic diagnosis before the index date. Additionally, if patients received any other antineoplastic drug before the initiation of any of the study drugs that is typically used for the 1L metastatic setting according to NCCN guidelines or expert knowledge, these patients will not be considered either (see list below*). This may decrease sensitivity as some of these drugs may be also used for the (neo)adjuvant setting but increase specificity in the selection of initiators in the 1L metastatic setting. More details and annotated code to identify initiators can be found in the 'Derive cohort EDB4' Quarto report (access within MGB network only).

*Antineoplastic drugs considered: afatinib, alectinib, amivantamab, atezolizumab, bevacizumab, brigatinib, cabozantinib, capmatinib, carboplatin, cemiplimab, ceritinib, cisplatin, cobimetinib, crizotinib, dabrafenib, dacomitinib, docetaxel, durvalumab, encorafenib, erlotinib, etoposide, fam-trastuzumab deruxtecan-nxki, gefitinib, gemcitabine, ipilimumab, larotrectinib, lorlatinib, mobocertinib, necitumumab, nivolumab, osimertinib, paclitaxel, pembrolizumab, pemetrexed, pralsetinib, ramucirumab, selpercatinib, tepotinib, trastuzumab, trastuzumab, trastuzumab-anns, trastuzumab-deruxtecan, trastuzumab-deruxtecan, trastuzumab-dkst, tremelimumab, vemurafenib, vinorelbine

Extract the date of first exposure => index date

Exclude patients who initiated more than one FLAURA drugs on the same date

Exclude patients who have received any other antineoplastic drug approved for advanced/metastatic NSCLC before their index date

Restriction to evidence of metastases before index date and general eligibility criteria

Figure 2. Identification of study drug initiators in EDB4

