Stage/TNM	Assessed date
Smoking	Assessed date

• EDB4: Time in {days, months and years} from index date to death due to any reason. The date of death is de-identified to month-level granularity and the day of death is therefore imputed to the 15th of a month. If there is no indication that a patient died during the study period, the patient is censored. The censoring date is defined as the last date of vital signs recorded as proof that the patient was alive at that time (de-identified to week-level granularity) or data cut-off date, whichever occurred earlier. The overall survival endpoint is operationalized using a parameterized R function edb4_get_os() and more details can be found in the attached pdf documentation.

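### In EDB4, patients who started treatment before 10/01/2018 are sampled on having survived to a later visit but followed from initiation; in sensitivity #11 this pushes the EDB4 hazard ratio upward.

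*Protocol*

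**What the plan says.** Four statements in the protocol, read together, define the EDB4 cohort and its survival clock.

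- **Sampling** (Table 3, section 6.1.1): "Patients with an office visit in the reporting period will be included in the report with full patient history". The study-period cell reads "Patient identification period: 10/01/2018-09/30/2023 with follow-up information through data cut-off date on 09/30/2023".
- **Cohort entry** (same table): "Anytime at start of study drug initiation". The wording is identical for all three databases and sets no lower bound at 10/01/2018.
- **Index date**: section 6.6.1 states "Time 0 in this database study is defined as the date a patient initiated osimertinib (exposure) or erlotinib or gefitinib (comparator"). For EDB4, section 6.6.4 adds "First, patients are identified who have ever initiated any of osimertinib, erlotinib or gefinitib", and Figure 2 takes the first exposure as the index date.
- **Outcome** (section 6.6.5, EDB4): "Time in {days, months and years} from index date to death due to any reason". No delayed entry is mentioned.

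Section 6.1.1 keeps EDB4 out of the main analysis for two related reasons: few controls from before osimertinib, and likely selection of patients who still started SoC after April 2018. EDB4 returns in sensitivity #11, where each database is analysed singly and the estimates are pooled with a fixed-effects model.

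**The concern.** This is left truncation without delayed entry. Someone who started in, say, 2017 and died before October 2018 cannot appear in EDB4. Someone who started the same day and lived long enough to be seen in the window does appear, and contributes the whole interval from 2017 as follow-up during which death could not have been observed.

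The arms are affected unequally. Section 4 states "Market availability of osimertinib began April 18, 2018", about five and a half months before the window opens, and sensitivity #9 speaks of only a few earlier osimertinib users. Starters well before the window are therefore nearly all SoC. Matching does not align start dates, because section 7 says calendar year cannot be balanced.

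The project's purpose is to judge concordance with FLAURA. An EDB4 or pooled HR moved toward 1 by this artefact could be read as discordance, and the fixed-effects pool would report it with a narrower interval.

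**Working it through.** **The plan's own figure.** The protocol gives no number for this problem. Its only related figure is 80% power in EDB1 (section 10.3: HR 0.8, two-sided alpha 0.05, Schoenfeld). Inverting it gives d = 4(1.960 + 0.842)² / (ln 0.8)² ≈ 631 events. The EDB1 event count is not in the text, so this is an implied value and not a check.

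**Does anything planned remove the problem?**
- #8 asks for a visit in the 90 days before initiation. It does not change when a patient enters the risk set.
- #9 drops only osimertinib users before April 18, 2018.
- #10 keeps starts from 2015 onward.
- Sections 6.1.1 and 7 do not list survivor selection.

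**Strength of the selection.** Under exponential survival with the FLAURA comparator median of 31.8 months (section 4), the chance that an SoC starter lives to 10/01/2018 is 2^(−m/31.8) for a start m months earlier:

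| m (months) | 6 | 12 | 24 | 36 |
|---|---|---|---|---|
| P(alive at window) | 0.88 | 0.77 | 0.59 | 0.46 |

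**Effect on the HR.** A simulation used a true HR of 0.80, an SoC median of 31.8 months, 15,000 patients per arm and a cut-off 60 months after 10/01/2018. Early starters were kept only if alive on 10/01/2018, a proxy for having a later visit. Shares are among retained patients. Shares and look-back spans are assumptions.

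| Early SoC starters | Early osimertinib starters | HR from initiation (as planned) | HR with delayed entry | SoC median, from initiation (months) |
|---|---|---|---|---|
| 0% | 0% | 0.81 | 0.81 | 31.6 |
| 10%, over 36 months | 0% | 0.85 | 0.80 | 33.8 |
| 25%, over 36 months | 0% | 0.93 | 0.80 | 37.0 |
| 25%, over 36 months | 10%, within 6 months | 0.91 | 0.79 | 36.9 |
| 25%, within 12 months | 10%, within 6 months | 0.81 | 0.78 | 33.2 |
| 50%, within 12 months | 10%, within 6 months | 0.87 | 0.79 | 34.0 |

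Delayed-entry fits scattered between 0.77 and 0.83 over all scenarios run, so the fair comparison is within a row. The simulation has no covariates and no matching.

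**Effect on the pool.** Assume 631 events in EDB1 at HR 0.80 and 300 in EDB4, with weights proportional to events (variance 4/d) and EDB2 left out for simplicity. Then ln HR(pooled) = [631 ln 0.80 + 300 ln HR(EDB4)] / 931.
- EDB4 at 0.85: (−140.8 − 48.8)/931 = −0.204, so the pooled HR is 0.82.
- EDB4 at 0.93: (−140.8 − 21.8)/931 = −0.175, so the pooled HR is 0.84.
- The standard error falls from √(4/631) = 0.080 to √(4/931) = 0.066.

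**The case against.** **Reach.** Tables 7 and 8 use EDB1 only. Section 6.1.1 already calls EDB4 insufficient for the main analysis, and #11 shows each database separately, so a deviant EDB4 estimate would be visible. This stands: no primary or secondary conclusion depends on the point. Visibility would not reveal the cause, though, because the protocol offers other explanations and not this one.

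**Size.** The early-starter share is not in the text, and Figures 8 and 15 are not available here. Section 6.1.1 says there are limited control "patients captured in EDB4 from the pre-osimertinib era (see Figure 15"). A reader might infer an EDB4 HR above 1. In the simulation that takes about 50% early SoC starters spread over 36 months (HR 1.06), and the documents give no basis for assuming so much. Few in number could still be a large share if later SoC starters are also few, but that is unknown.

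**Direction.** A reader might also infer that the EDB4 HR as a whole is biased against osimertinib. The documents support only the direction of this mechanism. Selection of patients who started SoC after approval acts on the same estimate in an unknown direction, and osimertinib starters from April to October 2018 are truncated too, a partial offset. The mechanism reversed clearly in the simulation only when early starts were more common and earlier in the osimertinib arm (0.71 with 30% of osimertinib starts over 36 months against 10% of SoC starts within 12). The availability date makes that implausible.

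**Interpretation.** Equating the reporting period with the identification period is an inference. Table 3 gives no other EDB4 period, and section 6.1.1 itself ties the 10/01/2018 start to the scarcity of early controls.

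**Conclusion.** The point holds as a flaw in the EDB4 part of sensitivity #11. Entry rule, index date and survival clock are all fixed in the protocol, and together they count guaranteed survival as time at risk, mainly in the SoC arm. Taken alone, this pushes the EDB4 HR upward. If the true HR is 0.80, plausible illustrations run from 0.81 to 0.93, and the pooled HR moves to about 0.82-0.84 for an EDB4 HR of 0.85-0.93.

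These sizes rest on exponential survival at the trial's SoC median, assumed early-starter shares and spans, and assumed event counts. The net bias in EDB4 is not determinable from the documents. The EDB1 primary and secondary results are unaffected. It is a modest point, but worth correcting before #11 is run.

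**What to change.** For EDB4 in sensitivity #11:

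1. Enter each patient into the risk set at the later of the index date and the first visit in the reporting period, in both the Cox model and the Kaplan-Meier estimate.
2. Report beside it an analysis restricted to index dates on or after 10/01/2018.
3. Amend the EDB4 cell of Eligible Cohort Entry Period to match, define the reporting period, and list the issue in sections 6.1.1 and 7.
4. State the number and share of EDB4 patients in each arm with an index date before 10/01/2018, so that the size can be judged.

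The programming and wording cost is small, but neither analysis is free of limits, and the protocol should say so. Delayed entry drops the few patients with no time at risk after their first in-window visit; censoring at the last vital-sign date and imputing death to mid-month can both cause this. Matching at index on survivor-selected early SoC patients can also leave residual bias, since their osimertinib matches are mostly followed from day 0. Restriction removes the truncation but loses the early SoC starters and leaves the later ones, whom section 6.1.1 suspects were selected for reasons that may not be measurable. Presenting both lets the reader see how far the EDB4 result depends on the choice.
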